To evaluate the safety and acceptability of the ShangRing for device-based circumcision in routine clinical settings, as a part of a comprehensive HIV prevention program for males aged 13 and older in Tanzania.

Evaluation Objectives

The specific objectives of the proposed implementation pilot is to:

- Describe/assess the safety of the ShangRing device by the occurrence of clinical adverse events (calculated as a rate), when circumcision is performed by trained mid-level providers;
- Ascertain capacity and required clinical capabilities of clinical staff of various cadres to carry out ShangRing procedures;
- Describe/assess male client and provider acceptability of the ShangRing device and process (e.g. need to return to the clinic for device removal, tolerance for leaving device in situ);
- Assess the percentage of clients clinically healed 6 weeks (42 days) following the removal of the device;
- Determine the time at which point all clients are physically healed following the removal of the device.

Primary Endpoint

The primary endpoint related to the goal and objectives of the evaluation is to:

- Measure the incidence of mild, moderate and severe AEs associated with ShangRing procedures including both procedure and post-procedure events, and all device-related malfunctions such as early spontaneous displacement. The primary endpoint will be assessed at device placement, at device removal, 3-days post removal, at the day 49 post-placement healing assessment, and at any unscheduled visit in that time frame. Adverse events will be measured and described in the following ways:
 - Total numbers and types of known AEs occurring among clients, including all severities of AEs (mild, moderate, severe) and serious AEs (see below), including detailed information about all instances of device displacement/detachment/self-removal/malfunction, need for medical attention or intervention, and final outcomes in those experiencing AEs.
 - Total number of clients with known AEs (may be different from above if clients experience multiple AEs), including all severities of AEs and serious AEs.

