Follow-Up Visits

Active follow-up will be initiated for clients who fail to return on day 7 post-placement to have the device removed, or for other visits (e.g. AE follow-up) recommended by the ShangRing clinician. Each implementing site will assign staff to conduct follow-up telephone calls and home visits as needed. All active follow-up efforts will be documented on the appropriate forms designed for this purpose (Appendix XI). For clients who fail to return for device removal on day 7, active follow-up will start on day 8. Active follow-up will start with telephone calls to the contact number(s) provided by client and recorded on the locator information sheet at enrolment. An

introductory script for contacting clients by phone is attached as Appendix X. If a client is not reachable through direct voice calls, short text message reminders will be sent to his contact phone number. The reminder text message will include client name and specify the name and phone number of the clinic reaching out to him. The text message will not include the purpose of appointment visit for which the reminder is sent. Up to five calls will be made to reach the client; one per day starting on day 8, and continuing over the next 4 days through Day 12 (5 days post-procedure).

Once contact is made, the staff member will reinforce the importance of device removal and encourage the client to return to the circumcision site. If the client states that he is not able to return by day 9 post-placement, or the schedule day, or does not in fact return by day 9 or the schedule day, the staff member will attempt to verify the addresses provided to schedule an appointment at one of the address locations provided for device removal on day 9, or as soon as possible. If the client has not been successfully contacted by day 9 or the scheduled day, home tracing visits to the address he provided will begin. These will total up to 4 visit attempts on different days if necessary to reach the client.

For clients not under follow-up for AEs who miss scheduled visits other than the day 7 visit, follow-up will be done through phone by text messages or voice calls only, except in exceptional circumstances where a clinician deems physical follow-up necessary.

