Data from the client's surgical and male circumcision medical records will be recorded on CRFs included in the Appendices (see Appendices VII and IX). The CRFs will be used to transfer the information collected in the performance of this evaluation to the clinical database. The original CRF will be kept in the clinic files and a copy will be maintained with additional documentation specifically for this evaluation including photographs, interviewer administered surveys and brief questionnaires. The hardcopy data will be entered into the evaluation database at each site. Corresponding forms, surveys and questionnaires will be completed immediately after each subject's visit. The site coordinator will review the CRFs for completeness and accuracy (signatures, dates, adverse events, serious adverse events, protocol departures) sign/date the forms where indicated. The evaluation team will retain originals of all source documents, subject consent forms, photographs and evaluation data as a permanent record.

The following data will be collected from clients receiving ShangRing circumcision:

Clinic Visit #1: Enrollment and Circumcision (Day 0)

- Documentation of general physical screening and medical examination on CRF
- Documentation of medication history on CRF
- Documentation of genital examination on CRF
- Documentation of device-related events and AE on forms, as needed
- Administration of evaluation survey after circumcision
- Collection of contact information from the client

Clinic Visit #2: Removal Visit (Day 7)

- Photographs of genitals after device removal
- Documentation of wound healing and genital examination on CRF
- Documentation of device-related events, AE and treatment and resolution of AE, as needed, on forms
- Documentation of changes to medical condition and medication on CRF
- Administration of evaluation survey after device removal

AE Assessment Phone Call (Day 10)

- Administration of an interview to determine whether client is experiencing signs and symptoms of an AE

Follow-Up In-Person Qualitative Interview (Day 28)

- For 50 clients
- Interview to determine client's feelings about ShangRing circumcision experience

Follow-Up In-Person Healing Assessment (Day 49)

- Documentation of wound healing and genital examination on CRF
- Photographs of genitals to document healing
- Documentation of device-related events, AE and treatment and resolution of AE, as needed, on forms

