Appendix XIII – Introductory script for contacting ShangRing clients by phone

Introductory script for contacting ShangRing clients by phone

May I please speak to _____?

If yes, proceed to next paragraph

If no, is there better time to call you later? If yes, schedule appointment follow another call

My name is _____ and I am calling from _____ (*name of health facility*) to follow up on your appointment to visit our clinic on _____ (*date*) for _____ (*purpose of missed appointment*). At your last visit to our clinic you indicated that you would come for _____ (*purpose of missed visit e.g. review or device removal*). May I ask if you may be available for this appointment at a different time?

Schedule another appointment for clinic visit or for home visit by providers depending on his availability.

If the client is not at home, but another person answers the phone, a message will not be left for the person who answers the phone. Proceed as follows;

My name is _____.

May I know when he is likely to be back for me to call him on this same number or can you guide me on how else I can reach him?

Depending on the response, schedule another call or follow guidance given on how to reach him.

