Appendix XIV – ShangRing Adverse Event Day 3 Post-Removal AE Check-in Call Form

ShangRing Adverse Event Check-in Call Form

Client ID:

Instructions

This form is to be used during the call with clients to check for signs of adverse events three days following the removal of the ShangRing device. The questions below are meant to evaluate whether the client is potentially experiencing an adverse event in the aftermath of their circumcision. After introducing yourself, and informing the client of the purpose of the call, ask the client each question on the list. For any 'yes' answers, probe for more information. If any of the information the client offers suggests an adverse event, advise that the client come to the clinic immediately for further evaluation.

Questions

1. Are you experiencing pain that keeps you from doing anything you normally do? **Y** **N**

a. **If yes:** Advise the client to visit the clinic to be evaluated

Note any comments: _____

2. Has swelling, tenderness or pain around the wound gotten worse since your circumcision? **Y** **N**

a. **If yes:** Advise the client to visit the clinic to be evaluated

Note any comments: _____

3. Have you noticed any expanding redness around the wound area, or red streaking spreading from the wound? **Y** **N**

a. **If yes:** Advise the client to visit the clinic to be evaluated

Note any comments: _____

4. Have you noticed any pus or fluid coming from the wound area? **Y** **N**

a. **If yes:** Advise the client to visit the clinic to be evaluated

Note any comments: _____

5. Have you felt like you have had a fever in the past few days, or experienced chills, shaking, breaking into sweats more than usual? **Y** **N**

a. **If yes:** Advise the client to visit the clinic to be evaluated

Note any comments: _____

6. Are you still bleeding from the wound area? **Y N**

a. **If yes:** Advise the client to visit the clinic to be evaluated

Note any comments: _____

7. Are you experiencing any difficulty urinating? **Y N**

a. **If yes:** Advise the client to visit the clinic to be evaluated

Note any comments: _____

8. Are you experiencing any other new problems since the surgery? **Y N**

a. **If yes:** Ask the client to describe the symptoms, and record below. If the symptoms are concerning advise the client to visit the clinic to be evaluated.

Note any comments: _____

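### Tracing calls to men who miss ring removal carry no question on ring status or symptoms, so an early detachment or self-removal in a man who then has no visit may go unrecorded

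*Protocol*

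**What the plan says.** **Tracing.** Under Follow-Up Visits, a man who misses the day 7 removal is called once a day from day 8 to day 12. Home tracing begins if he has not been contacted by day 9 or the scheduled day, with up to four attempts. On a successful call, "Once contact is made, the staff member will reinforce the importance of device removal and encourage the client to return to the circumcision site". If he cannot or does not come by day 9, staff verify his addresses "to schedule an appointment at one of the address locations provided for device removal on day 9, or as soon as possible".

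**Script.** Appendix XIII names the missed appointment and asks: "May I ask if you may be available for this appointment at a different time". The caller is then told: "Schedule another appointment for clinic visit or for home visit by providers depending on his availability".

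**Symptom checklist.** Appendix XIV opens: "This form is to be used during the call with clients to check for signs of adverse events three days following the removal" of the device. Its eight questions cover symptoms; none asks about the ring.

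**Endpoint.** The Primary Endpoint section requires "detailed information about all instances of device displacement/detachment/self-removal/malfunction". The Executive Summary names early spontaneous detachment as an example of a device malfunction counted in the primary endpoint. Appendix XIX grades self-removal as moderate or severe, with no mild category. The listed AE assessment points are placement, removal, three days after removal, the day 49 visit, and unscheduled visits in that period.

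**Forms.** Follow-Up Visits states: "All active follow-up efforts will be documented on the appropriate forms designed for this purpose (Appendix XI", closing the bracket there. Appendix XI is now the Post-Removal Survey. The same section cites Appendix X for the script; Appendix X is now the Post-Placement Survey.

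**Counting.** The Lost-to-Follow-Up section says that men lost after placement who do not return for removal are neither recorded as having an AE nor included in the AE calculation.

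**The concern.** A man whose ring has come off, or who took it off himself, has an evident reason to miss a removal appointment. Some of the detachments and self-removals that the endpoint must capture may therefore lie among the men being traced. The protocol pays for the contact and then scripts only a rebooking conversation. If he declines to come in because there is nothing left to remove, capture depends on his volunteering what happened and on the caller knowing where to write it down. At stake are the completeness of the primary safety endpoint and the chance to learn of a problem in a man already on the telephone.

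**Working it through.** **1. What each contact is told to ask or record**

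| Contact | Ring status | Symptoms or AE | Source |
|---|---|---|---|
| Tracing call after missed removal | not stated | not stated | Follow-Up Visits; Appendix XIII |
| Home tracing visit | not stated (a removal appointment would show it) | not stated for the tracing attempt | Follow-Up Visits |
| Off-site removal by a provider | seen at removal | removal-visit AE documentation | Follow-Up Visits; Data Collection; Appendix XII |
| Call three days after removal | no item | eight questions | Appendix XIV |
| Call started by the client about an AE | not stated | clinical course and AE discussed | Telephone Calls Initiated By Clients due to AEs |
| Day 49 visit | not applicable | AE documentation | Data Collection |

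The protocol provides for AE content by telephone in two other kinds of call, but not in tracing calls for missed removal.

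**2. Who falls through.** A man who returns late, has the ring removed off-site or attends day 49 meets an AE assessment. The gap is confined to men with telephone contact only and to tracing visits whose content is not stated.

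**3. The plan's own precision figure.** With p = 0.02, half-width d = 0.015 and 95% confidence (Sample Size section):

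n = 1.96² × 0.02 × 0.98 / 0.015² = 334.6, rounded up to 335. This reproduces the stated minimum.

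At n = 575 the half-width is 1.96 × √(0.02 × 0.98 / 575) = 1.14 points. Expected clients with an AE: 0.02 × 575 = 11.5.

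**4. Effect of missed events.** Two missed clients: 2/575 = 0.35 points.

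More generally, let M men be left uncounted with event risk q, and let counted men have a 2% rate. The rate in all 575 is [0.02 × (575 − M) + q × M] / 575, so the understatement is M × (q − 0.02) / 575. The protocol gives neither M nor q; both are assumed here.

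| M (share of 575) | q = 0 | q = 2% | q = 10% | q = 25% | q = 50% |
|---|---|---|---|---|---|
| 12 (2%) | −0.04 | 0 | 0.17 | 0.48 | 1.00 |
| 29 (5%) | −0.10 | 0 | 0.40 | 1.16 | 2.42 |
| 58 (10%) | −0.20 | 0 | 0.81 | 2.32 | 4.84 |

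Entries are percentage points; negative means the reported rate is too high. The direction depends wholly on whether q exceeds 2%. The table overstates what better calls could recover, because M includes men whom nobody reaches.

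**The case against.** **The script is only an introduction.** It is generic, it opens the call, and an SOP manual exists that may say more. Silence is not a prohibition. This is fair, but the protocol does state what follows once contact is made, and that text adds no such question.

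**A form already covers these contacts.** The Follow-Up Form (Appendix XII) is meant for all follow-up visits, codes phone and off-site contacts, and asks whether an AE was seen or reported. This stands in part: a recording place exists. However, its instructions speak of visits, its visit types do not include a tracing contact, it has no item on whether the ring is in place, and the tracing section points to another appendix. The columns of the Appendix XV follow-up log are not in the available text, so a ring-status field there cannot be ruled out.

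**The checklist call is also labelled day 10**, which falls inside the tracing window, and one could make it to every man. But its form presupposes a removal.

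**Other routes exist.** Clients are told to return or make contact if the ring comes off, and all are invited to day 49. These shrink the gap without closing it.

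**The exclusion rule matters more.** If it covers a man who was reached but never returned, asking him questions would not change the rate. This stands, and it is why the fix must include that rule.

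**Conclusion.** The point holds as a limited gap in ascertainment. Following the printed text, a man reached by phone who has lost or removed his ring and then has no visit has no scripted route into the primary endpoint. Its size is unknown: two such clients would be about 0.35 points, against an expected 2% and a half-width of 1.14 points.

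Three stronger readings are tempting but not supported:

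- **Home visits only rebook.** The off-site appointment is for device removal and the scheduled home visit is made by providers.
- **These are the highest-risk men.** The Lost-to-Follow-Up section cites a study with no severe or serious AEs among men who wore the ring beyond seven days. It treats later detachment as the usual course, so not every ring found off is an endpoint event.
- **The rate is biased low by a stated amount.** Bias requires event risk above that of counted men, and the protocol gives no non-return rate or detachment proportion from which to compute it.

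**What to change.** 1. In Follow-Up Visits and Appendix XIII, add to every successful tracing contact: is the ring in place and, if not, when and how did it come off; then the Appendix XIV symptom questions.
2. Require the Follow-Up Form at each such contact (phone or off-site contact type, with a tracing option among the visit types) and, where relevant, the device events form. Flag events that are self-reported and not examined.
3. Add tracing contacts to the AE assessment points under Primary Endpoint.
4. Correct the outdated references to Appendices X and XI in Follow-Up Visits.
5. Reconcile three passages so that events learned by tracing are counted: the exclusion of men who do not return for removal (Lost-to-Follow-Up), the requirement to detail all detachments and self-removals (Primary Endpoint), and the default moderate AE for untraceable men who had phoned about an AE (Telephone Calls Initiated By Clients due to AEs).

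The cost is a few lines of text and a short addition to contacts already planned. The downside is that some events will rest on self-report without examination; the flag in item 2 allows the rate to be shown with and without them. The change concerns data collection only.

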Evaluation Goal:

To evaluate the safety and acceptability of the ShangRing device for nonsurgical circumcision in routine clinical settings, as a part of a comprehensive HIV prevention program for males in VMMC programs.

Evaluation Endpoints:

Primary Endpoint: the proportion of males experiencing mild, moderate and severe adverse events (AEs) associated with ShangRing circumcision procedures, including both intra- and post-operative events, and all device-related malfunctions (e.g., early spontaneous detachment).

Secondary Endpoints:

- Training needed for proficiency using the ShangRing device, including number of procedures to become fully proficient at applying and removing the ShangRing device.
- Client and provider acceptability, client satisfaction, and duration of procedure.
- The percentage of clients clinically healed 49-52 days post-placement of the ShangRing device, and the time at which point all clients are clinically healed.

Evaluation Design

Training Phase: this phase will be used to evaluate the training requirements for implementation by mid-level providers, to preliminarily assess acceptability to providers, and to monitor logistical needs. Each clinician will perform no fewer than 10 ShangRing device placements, and 5 ShangRing removals before start of the next phase (implementation pilot).

Implementation Pilot: following the training period, 575 male clients will be recruited to undergo circumcision with the ShangRing device in the context of routine service delivery.

Data will be collected at up to at least 5 points in time: at enrollment and device placement (day 0), at device removal (day 7), during a follow-up phone call (day 10), in-depth qualitative interviews for 50 purposefully selected clients (day 28), at an in-person follow-up visit to assess wound healing (day 49), and at subsequent weekly visits to assess healing for those not completely healed at day 49.

Upon completion of the implementation pilot, the data will be analyzed and used to assist with policy decisions and recommendations on ShangRing use in adult male circumcision programs.

Section C: Protocol

Introduction

Voluntary Male Medical Circumcision (VMMC), VMMC Devices and ShangRing

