Procedure for Handling Clients Lost-to-Follow-Up

Clients who are lost to follow-up after device placement, and therefore do not return to have the device removed, will not be recorded as experiencing an AE, and also will not be included in calculations when measuring AEs.

In the event that a client refuses to return for follow-up, ShangRing has been shown to detach on its own. Studies show that for those clients who do not come in to have the device removed, and wear it for more than

seven days, the ShangRing will eventually spontaneously detach on its own, and healing will progress normally. In one study, complete detachment of the device occurred in 66.7% of men who wore the device for more than seven days, and 14% of men requested removal of a partially detached device 8-14 days after placement. No severe or serious AEs were reported among this group.²⁹

A study of delayed removal of ShangRing in Kenya found that in 81.8% of men the ShangRing had completely detached on its own between 10-16 days after circumcision.³⁰ By 21 days following the circumcision the ring had at least partially detached in 100% of men, and was completely detached in 93.7%. While the ShangRing has been found to be safe if left on, this is not the recommended standard of care for the purposes of this evaluation, and clients will be followed up with for device removal as described in this protocol.

Provider Participant Inclusion Criteria

Providers meeting the following criteria will be included in the evaluation:

- Adult aged 18 or older
- Employed as a medical doctor, Assistant Medical Officer, Clinical Officer, professional nurse, or enrolled nurse at the participating sites in Shinyanga, Tanzania
- Experienced in providing conventional surgical circumcision
- Trained and certified in ShangRing circumcision techniques for the current evaluation by a trainer who is trained in ShangRing application, and has performed a minimum of 10 placements and 5 removals. The evaluation team will bring in ShangRing master trainers from countries with prior ShangRing experience (i.e. Kenya, Zambia) to train providers based in Shinyanga who will then train mid-level providers to conduct ShangRing circumcision, or send physicians from Tanzania to these countries for training.
 - Trained and competent in identifying and managing complications related to ShangRing circumcision.
 - Trained and competent in screening clients to determine their eligibility for ShangRing circumcision.

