All clients in the evaluation will be followed up at three points in time following ShangRing circumcision, on day 7 (device removal), on day 10 (three day post-removal AE assessment phone call), and day 49 (42 days/6 weeks following device removal). Ten percent of all clients will be brought in on day 28 (21 days/3 weeks following device removal) for in-depth qualitative interviews.

At the day 49 visit, a clinician will assess healing, an evaluation staff will photograph the client's genitals to document healing, and the client will receive counseling that will stress the following messages:

- If the wound is considered to be healed, the client will be informed that they may resume sexual activity and masturbation, but counseled on the need to continue safe sexual practices.
- If the wound is not considered healed, the clinician will offer ask the client to return in one weeks' time to assess healing and ensure the wound is fully healed. The client will also be advised to continue abstention from sexual activity and masturbation.
- If the client is not considered healed, and there is a clinically indicated reason to schedule further follow-up to take place before the next weekly visit, the evaluation staff will schedule such follow-up visits at a medically appropriate time.
- All sexually active clients will be offered a package of condoms to take home.

One week preceding the day 49 healing assessment visit (day 42) the client will receive a short reminder text asking that the client contact the site to confirm the appointment. The reminder text message will include client name and specify the name and phone number of the clinic reaching out to him. The text message will not include the purpose of appointment visit for which the reminder is sent. The client will be asked to confirm the appointment by either calling the clinic, or by replying with a text. If the client does not confirm the appointment within 3 days, (day 45), the client will be sent a second text. If the client still has not confirmed the appointment by day (47), the client will receive one phone call per day from day 47-49 until they have confirmed the appointment or indicated their intent not to come. If the client does not come in on day 49 for the healing assessment visit, and has not indicated his desire to withdraw from the evaluation, then the client will be established as lost to follow up.

Post Day 49 Healing Assessment Visits

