Baseline demographics and client characteristics will be presented in tabular format using descriptive statistics. Binary data such as adverse events will be presented as counts and percentages and the upper limit of the estimate of the AE rate (percent of clients with one or more AE) will be based on a two-sided 95% confidence interval. Adverse event rates will be compared descriptively with the reported rates of similar treatments reported in Tanzania and elsewhere, including: comparison against AE rates found in other studies of ShangRing, comparison against AE rates found in studies of other circumcision devices, and comparison against reported rates of AEs in studies of surgical circumcision. No formal hypothesis tests will be done comparing AE rates in this evaluation to other AE rates.

Adverse event rates will be presented by seriousness, severity, relation to device and outcome by site and by cadre. Continuous data will be represented by a mean, standard deviation, median, minimum and maximum together with 95% confidence intervals for the means. The number and percent of subjects who fail to complete the evaluation will be assessed. Time to withdrawal may also be assessed. The procedure time will be calculated. The first 15 procedures performed by each provider will be compared to the last 15 procedures by that provider with respect to procedure time, to evaluate whether procedure time is shortened with experience. All of the first and last 15 procedures evaluated will take place during the main implementation pilot phase. If a provider does not perform 30 total procedures following the training phase, then the first half of the total number of procedures performed will be compared against the last half. Adverse event rates from the training and post-training phases will also be reported, as well as an overall AE rate. Procedure times during the provider training phase will be tracked, but not used for comparisons. The differences in mean procedure times will be compared with a t-test or a non-parametric equivalent.

Standard statistical software packages R, Stata or SAS will be used for the analysis. No corrections for missing values will be imputed. The data will be analyzed and presented “as-is”.

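### Men lost after ring removal have no stated place in the AE rate; read literally they count as AE-free, so missed post-removal AEs lower the rate and its upper limit

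*Protocol*

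**What the plan says.** The primary endpoint in the Executive Summary is "the proportion of males experiencing mild, moderate and severe adverse events (AEs) associated with ShangRing circumcision procedures". On timing, the Primary Endpoint section says: "The primary endpoint will be assessed at device placement, at device removal, 3-days post removal, at the day 49 post-placement healing assessment", and it adds unscheduled visits within that period.

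The Analysis Overview fixes the estimator: "the upper limit of the estimate of the AE rate (percent of clients with one or more AE) will be based on" an interval with two-sided 95% coverage. On missing data it says: "No corrections for missing values will be imputed. The data will be analyzed and presented" as they stand.

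Four rules deal with men whose follow-up is incomplete:

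- **Lost before removal** (Procedure for Handling Clients Lost-to-Follow-Up): men who are lost "and therefore do not return to have the device removed, will not be recorded as experiencing an AE", and they are also left out of the AE calculations.
- **Missing day 49** (Follow-Up Visits): "If the client does not come in on day 49 for the healing assessment visit, and has not indicated his desire to withdraw", he is classed as lost to follow-up. Nothing is said about the AE numerator or denominator. For men not under AE follow-up who miss a visit other than day 7, "follow-up will be done through phone by text messages or voice calls only", with an exception where a clinician judges a physical visit necessary.
- **Withdrawn after placement** (Client Withdrawal Criteria): data already collected stay in the analysis, and collection stops apart from clinical documentation of the removal visit.
- **Untraceable after phoning about an AE** (Telephone Calls Initiated By Clients due to AEs): if a medically indicated visit is missed and tracing fails, a moderate AE is assumed by default.

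**The concern.** A proportion without imputation needs a rule on who belongs in its denominator. The protocol gives one for loss before removal and none for loss after removal. The man in question attends day 7, is not reached on day 10 and does not come on day 49. By the literal wording he is a client without an AE, although no scheduled contact looked for one after removal. A man reached on day 10 but absent on day 49 is in a similar position for the later weeks.

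This matters because some AE types appear mainly after removal. Appendix XIX lists wound disruption only in the block for events during or after removal. In the cited field study (Table 1) wound dehiscence made up 9 of the 18 AEs in HIV-negative men.

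Under that reading the error has one direction: an unseen AE can only lower the rate. The rate is the primary safety result. It will be set beside surgical and other device rates and is meant to inform national policy.

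The rules can also collide. A man who phones about a problem while wearing the ring and is then never found fits both the exclusion and the default moderate AE.

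**Working it through.** **1. The protocol's own figure.** Sample Size gives an AE rate of 2%, a margin of ±1.5 points, 95% confidence and a minimum of 335. The single-proportion formula is n = 1.96² × p(1 − p) / d². With p = 0.02 and d = 0.015, n = 1.96² × 0.0196 / 0.000225 = 334.6, so 335. This reproduces, and 335 + 240 = 575. The half-width at 575 is 1.96 × √(0.02 × 0.98 / 575) = 1.14 points, so the upper limit at 2% is 3.14%.

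**2. Dilution under the literal reading.** Let L be the share of clients who miss both post-removal contacts (day 10 and day 49), and f the share of AEs that first appear after removal. If these men have average risk and none of their late AEs comes to light, then

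observed rate = true rate × (1 − f × L).

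The protocol gives neither L nor f, so both are assumptions. With a true rate of 2%:

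| L | f = 0.25 | f = 0.50 | f = 0.75 |
|---|---|---|---|
| 5% | 1.98% | 1.95% | 1.93% |
| 10% | 1.95% | 1.90% | 1.85% |
| 20% | 1.90% | 1.80% | 1.70% |
| 30% | 1.85% | 1.70% | 1.55% |

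At f = 0.50 the upper limit at N = 575 falls from 3.14% to:

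- 3.02% at L = 10% (1.90 + 1.12)
- 2.89% at L = 20% (1.80 + 1.09)
- 2.76% at L = 30% (1.70 + 1.06)

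**3. AEs found outside the schedule.** If a share c of the late AEs in these men is caught at unscheduled visits, by client calls or through alerts from other clinics, the factor becomes 1 − f × L × (1 − c). With f = 0.5, L = 20% and c = 0.5 (assumed), the rate is 2% × (1 − 0.05) = 1.9% rather than 1.8%.

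**4. Loss related to risk.** If the lost men had twice the late risk (f = 0.5, L = 20%), the true rate would be 2% + 0.20 × 0.5 × 2% = 2.2%. Counting them as AE-free gives 1.8%, and leaving them out gives 2.0%. Neither choice removes the bias, which is why bounds are needed as well as a rule.

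**5. Cost in precision of a day-49 denominator.** At a rate of 2%, with 5%, 10%, 20% or 30% not assessed, N is 546, 518, 460 or 402. The half-width is 1.17, 1.21, 1.28 or 1.37 points, against 1.14 at 575.

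**The case against.** The strongest reply is that the protocol never says these men count as AE-free. Follow-Up Visits only attaches a label, an analyst could extend the pre-removal exclusion to them, and a statistical analysis plan might settle the matter. The first part stands: the treatment is inferred from the estimator and the no-imputation rule. The last part carries less weight, because the protocol itself fixes the estimator, the ban on imputation and an exclusion for one class of loss, and these do not cover the other class. Extending the exclusion would not be harmless either, since it could drop men whose AE was already recorded.

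A reader might infer more than the documents support:

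- *That excluding men lost before removal also dilutes the rate.* It does not. They leave numerator and denominator together. The risk there is selective loss of events during wear.
- *That every man lost later was observed for only 7 of 49 days.* This holds only for men also missed on day 10. Men are told to come back with problems, neighbouring health centres are asked to alert the sites, and AEs found at unscheduled visits count.
- *That at least half of AEs arise after removal.* The 9 of 18 comes from a cohort with no mild AEs in HIV-negative men, where 19 cutaneous pinches lay outside the AE definition. This evaluation counts mild AEs and placement events, so f could be well below 0.5.
- *That the upper limit decides policy.* No threshold or formal test is attached to it.

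Large values of L are also unproven. Clients need access to a phone, receive reminders and are reimbursed for day 49, and the number failing to complete will be reported. That report shows how many were lost, but not what the AE rate is among those assessed.

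**Conclusion.** The point holds as a gap with a one-directional consequence. The protocol fixes the AE denominator for loss before removal and leaves it unstated for loss after removal. Under the literal estimator, post-removal AEs missed in men lost later bias the primary rate and its upper limit downward.

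The size is modest and cannot be settled from the protocol. For a true 2%, f = 0.5 and L = 10% to 30% give 1.9% to 1.7%, a shift of 0.1 to 0.3 points. Across the grid above the shift runs from about 0.03 to 0.45 points. Each value supposes average risk in the lost men and no capture outside the schedule. Capture makes the shift smaller, and higher risk among the lost makes it larger. All values lie below the 1.14-point half-width, but that interval reflects sampling error only and does not show this bias.

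This should be corrected before analysis. It does not invalidate the design, and the all-client proportion need not be replaced.

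**What to change.** In the Analysis Overview:

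1. Keep the all-client proportion as the main rate, with every known AE counted. State one denominator rule that covers each class: lost before removal, lost after removal, withdrawn after placement, and untraceable after an AE call. Reconcile the sections on withdrawal, loss to follow-up, follow-up visits and client-initiated calls with it.
2. Report AE rates by scheduled contact (placement, removal, day 10 call, day 49) with the number assessed at each. Show AEs found at unscheduled contacts separately. A denominator of men with any later contact would admit some men because they had an AE, and would push the rate upward.
3. Add a sensitivity rate among men assessed at day 49.
4. Add bounds for men with no post-removal contact. The extreme bound is wide: with 12 AEs in 575 and L = 10%, it runs from 2.09% to (12 + 57.5)/575 = 12.09%. Intermediate cases are therefore useful, such as the post-removal rate seen in assessed men and twice that rate.

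A life-table estimate to day 49 may be added as support. It assumes that loss is unrelated to AE risk, and it would rest on dates of diagnosis, so it need not become the main rate.

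The contact data are already collected. The cost is revised wording, a little more analysis, and sensitivity rates that are likely to be slightly higher with wider intervals.
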